## 10.8.2 Subject Eligibility

Subject's eligibility for the clinical trial will be checked according to the inclusion and exclusion criteria at visits specified in the flowchart, cf. 10.8.1. Subjects' demographic details and duration of scalp psoriasis will be recorded.

Concomitant medication and medical history are recorded at SV1 and changes in concomitant medication are recorded at all subsequent visits.

### *Demographic Data*

Demographic data will comprise of:

Date of birth

Sex

Ethnic origin

Race

Skin type

The subjects will self-report their ethnicity (Hispanic or Latino, not Hispanic or Latino) and race (American Indian or Alaska Native, Asian, Black or African American, Native Hawaiian or Other Pacific Islander, White, Other).

The skin type of the subject will be recorded according to the following classification and can be assessed by the (sub)investigator or research nurse:

### **Fitzpatrick Skin Type**

Skin Type	Skin Colour (unexposed skin)	History (to first 30 to 45 minutes of sun exposure after a winter season of no sun exposure)
I	White	Always burns easily; never tans
II	White	Always burns easily; tans minimally
III	White	Burns moderately; tans gradually (light brown)
IV	White	Burns minimally; always tans well (moderate brown)
V	Brown	Rarely burns; tans profusely (dark brown)
VI	Black	Never burns; deeply pigmented

***Height and Weight***

The subject's weight (with indoor clothing and without shoes) will be recorded in kg and the height (without shoes) will be recorded in cm.

***Duration of psoriasis vulgaris***

The duration of psoriasis vulgaris will be recorded to the nearest whole year.

***Relevant Medical History, Concomitant Medication and Concurrent Diagnoses***

Relevant medical history, concomitant medication and concurrent diagnoses will be recorded.

***Physical Examination***

Physical examination will consist of: Routine medical examination including gross neurological assessment and other appropriate system.

***Vital Signs***

Recording of vital signs comprises:

- Heart rate (beats per minute), supine after 5 min rest
- Blood pressure, systolic and diastolic (mmHg), supine after 5 min rest

The same arm will be used for all measurements. The arm (right or left) used for measurement will be recorded in the CRF.

Assessment of vital signs resulting in abnormal values will be repeated in order to exclude an erroneous assessment. Individual results will be classified as "normal", "abnormal with no clinical significance" or "abnormal with clinical significance".

***Dietary calcium intake – diary instructions***

The (sub)investigator/site staff should perform a review of the subject's normal dietary intake of calcium-rich nutrients – mainly milk and dairy products, but also a high intake of calcium-fortified products. The subject will be instructed to keep a diary of the daily intake of calcium-rich nutrients in the 4-day period prior to SV2 (3 days prior to and during the baseline 24-hour urinary collection).

At SV2, the number of daily servings of dairy (or calcium fortified) products defined as one cup (240 ml) of milk or yoghurt, 1.5 ounces (43 g) of cheese or any calcium-fortified product with a calcium content of 300 mg/cup will be estimated. The subject will be instructed that the number of daily calcium servings should not exceed five. Also the subject should keep the intake of calcium-rich nutrients the same three days prior to and during each subsequent 24-hour urine collection. At the following visit, i.e. Visit 3 and Visit 5 respectively, the (sub)investigator/site staff should review the intake of calcium-rich nutrients with the subject. Based on the diary entries the (sub)investigator/site staff should estimate the number of daily calcium servings for each day and these will be recorded in the CRF.

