Calcium metabolism will be evaluated in the present study by 24-hour urinary collection and measurement of serum calcium, -phosphate and plasma PTH before, during and/or after treatment. 24-hour urine will be collected and the urinary calcium-, phosphate- and creatinine excretion will be measured and the calcium:creatinine and phosphate:creatinine ratios calculated. Subjects who report an incomplete 24-hour urinary collection will be excluded from the analyses of 24-hour urinary calcium and phosphate excretion but will still be analysed for calcium:creatinine and phosphate:creatinine. To identify any severe, non-reported sampling errors the daily creatinine excretion/kg body weight will be calculated as proposed by Remer et al. (32).

It is well established that there is a relationship between dietary calcium intake and the urinary calcium excretion in adults. However, in rapidly growing adolescents, it appears that only dietary calcium intake above a certain threshold of approximately 1500 mg/day will result in an increase in urinary calcium excretion (33). As this study includes adolescents 12 to 16 years, 11 months of age, some of the subjects may not be in phase of rapid growth and some subjects might consume large amounts of dairy products. Therefore, there is a possibility of an effect of the diet on the calcium excretion.

A review of the subject's normal diet will be done. As dairy products account for approximately 73% of the total dietary calcium content, and as the calcium from other sources such as vegetables and grains are less easily absorbed (34), the review will focus on the intake of dairy products. The subjects will be asked to keep a diary of the daily intake of dairy products and calcium-fortified products (e.g. bread, cereals, orange juice or soy milk). The number of daily servings of calcium defined as one cup (240 ml) or 1.5 ounces of cheese (43 g) in dairy products such as milk, yoghurt or cheese or of a calcium-fortified product with corresponding calcium content (300 mg calcium/cup) will be estimated (35). The subjects will be asked to keep the same number of daily servings three days prior to and during each 24-hour urine collection. The number of daily calcium servings should not exceed five (i.e. 1500 mg calcium).

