#### **10.8.4 Laboratory Assessments**

##### **10.8.4.1 Central Analysis**

Samples for analysis of the parameters listed below will be taken as scheduled in the flowchart (cf. 10.8.1) or at early withdrawal from the treatment period of the study.

It is recommended that indwelling catheters introduced under topical anaesthesia are used for the repeated blood sampling, to minimise discomfort for the subject, unless the (sub)investigator judges that there are reasons for not doing it.

A 6.5 ml sample of venous blood and a 30 ml spot urine sample will be taken at SV2, Visit 3 and Visit 5. The 6.5 ml sample of blood will consist of 2 ml for haematology analysis, 2.5 ml for serum biochemistry analysis and 2 ml for analysis of plasma parathyroid hormone. The samples will be taken before the ACTH-challenge test that is also scheduled for these visits (for U.S. only). Measurement of serum cortisol concentration will be included in the biochemistry analysis, and this value will be the baseline serum cortisol concentration for the ACTH-challenge test.

At Visit 3, a 12mL (2 x 6 mL) blood sample will be taken for pharmacokinetic analysis.

Prior to SV2, Visit 3 and Visit 5, subjects will collect 24 hour urine. It is allowed to collect the 24-hour urinary sample up to three days prior to the study visit.

The Central Laboratory will provide the materials and instructions necessary for the collection and transport of the samples.

The following analyses will be performed on the blood samples:

Haematology

Haemoglobin

Haematocrit

Red blood cell (RBC) count

Mean corpuscular volume (MCV)

White blood cell (WBC) count, including differential count

Platelet count

Serum/plasma Biochemistry

Cortisol

Urea

Creatinine

Albumin  
Sodium  
Potassium  
Chloride  
Calcium  
Phosphate  
Parathyroid hormone (plasma)

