Appendix 2.7: Safety Data

Listing 7-1 Deaths

Listing 7-2 Serious Adverse Events

Listing 7-3 Subjects withdrawn due to AE

Listing 7-4 Severe Adverse Events

Listing 7-5 Adverse Events

Trial ID: LP0076-1017	Date: 16-Mar-2018	Version: 1.0 Page 27 of 27
-----------------------	-------------------	-------------------------------

Listing 7-6 Dietary Calcium Intake

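### Protocol sections 10.8.2, 8.3 and 3.1 do not agree on whether the five-serving calcium cap applies before the baseline 24-hour urine; for subjects above five servings this can bias the change in urinary calcium downwards

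*Protocol*

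**What the plan says.** Protocol section 10.8.2 (dietary calcium intake) has two steps. The first concerns the run-up to SV2: "The subject will be instructed to keep a diary of the daily intake of calcium-rich nutrients in the 4-day period prior to SV2". Those four days include the baseline urine collection, and no limit on servings is mentioned. The second step is introduced as taking place at SV2. Servings are estimated, then "The subject will be instructed that the number of daily calcium servings should not exceed five", and "the subject should keep the intake of calcium-rich nutrients the same three days prior to and during each subsequent 24-hour urine collection". Section 10.8.4.1 fixes the timing of the samples: "Prior to SV2, Visit 3 and Visit 5, subjects will collect 24 hour urine".

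Two other places read differently. Section 8.3 says "The subjects will be asked to keep the same number of daily servings three days prior to and during each 24-hour urine collection" and then "The number of daily calcium servings should not exceed five (i.e. 1500 mg calcium"), with no visit attached to the cap. The schedule in section 3.1 marks instruction on urine collection and the diet diary at SV1, Visit 2 and Visit 4. At SV2 it marks only a review of dietary calcium.

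Section 8.3 also gives the reason for the cap. In cautious terms, and for adolescents in a phase of fast growth, it reports this: "only dietary calcium intake above a certain threshold of approximately 1500 mg/day will result in an increase in urinary calcium excretion". The section adds that some subjects may not be growing rapidly, that some may eat a lot of dairy, and that diet may therefore affect excretion.

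In the SAP, dietary intake appears only as "Listing 7-6 Dietary Calcium Intake". No planned table uses it.

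**The concern.** Change in 24-hour urinary calcium from SV2 is a primary response criterion (protocol 10.9.1), and the trial has no control group. Nothing in the design separates a change in diet from a drug effect. If a site follows 10.8.2 in order, a subject who eats more than five servings a day gives the baseline urine on that diet and is then told to stay at five or below. The same subject is told to keep intake unchanged, so the two instructions conflict.

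A subject who follows the cap lowers calcium intake after baseline, down to the level above which section 8.3 says excretion responds. Urinary calcium can then fall for a reason unrelated to treatment. That direction would offset a rise caused by calcipotriol. The calcium:creatinine ratio (secondary, 10.9.2) uses the same urinary calcium, and the shift tables compare against the same baseline.

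**Working it through.** **1. The cap and the threshold.** Section 8.3 gives 300 mg calcium per serving. 5 × 300 mg = 1500 mg/day, which reproduces the stated figure and equals the threshold in the same section.

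**2. The order of events.**

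| Place | Before the baseline urine | At or after SV2 |
|---|---|---|
| 10.8.2 | Diary only; no cap named | Cap; same intake for later collections |
| 10.8.4.1 | Baseline urine collected | Urine before Visits 3 and 5 |
| 8.3 | Same servings for every collection; cap with no visit | Same |
| Schedule 3.1 | Instruction at SV1 (collection and diary; cap not named) | Review at SV2; instruction at Visits 2 and 4 |

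Section 10.8.2 alone points to a cap given after the baseline urine. Section 8.3 can be read as applying it to all three collections. The SV1 entry in the schedule fits either reading.

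**3. Who is affected.** A subject at or below five servings at baseline only has to keep intake the same, so the cap adds no bias. A subject above five servings faces the conflict. If the cap comes before baseline and is followed, both the conflict and the bias disappear.

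**4. Possible size.** The documents do not give the share of subjects above the cap, their excess, the fraction of excess calcium excreted, or the SD of the change. All four are assumptions here.

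Shift per affected subject = excess servings × 300 mg × fraction excreted. With 1 to 3 excess servings and 3% to 10% excreted:
- lowest: 1 × 300 × 0.03 = 9 mg/day
- highest: 3 × 300 × 0.10 = 90 mg/day

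Shift in the mean change = −(share above the cap) × (shift per affected subject):

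| Share above five servings | Mean shift, mg/day |
|---|---|
| 0% | 0 |
| 5% | −0.45 to −4.5 |
| 10% | −0.9 to −9 |
| 30% | −2.7 to −27 |

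**5. Compared with the precision of the mean.** SAP Table 3 gives 92 urinary calcium observations at Week 4 and 79 at Week 8. Half-width of the 95% interval = t(0.975, n−1) × SD/√n. With an assumed SD of 40 to 120 mg/day:
- n = 92: 8.3 to 24.9 mg/day
- n = 79: 9.0 to 26.9 mg/day

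Nine baseline values are also missing, so the number of pairs may be smaller and the half-widths somewhat larger.

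With 90 mg/day per affected subject, the shift reaches the Week 4 half-width when 8.3/90 = 9% of subjects are above the cap (SD 40), or 24.9/90 = 28% (SD 120). At mid-range values (2 servings, 6% excreted, so 36 mg/day; SD 80, half-width 16.6) it would take 16.6/36 = 46% of subjects.

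**The case against.** The strongest objection is that the documents nowhere say the baseline is uncapped. Section 8.3 attaches the same-servings rule to every collection, and instruction on diet and urine collection is scheduled at SV1. In 10.8.2 the cap sentence has no time marker of its own. This stands as far as it goes, and it makes the point an inconsistency. It does not remove it: the SV1 entry names the diary and the collection but not the cap, and the paragraph order and the word for later collections in 10.8.2 favour a cap given at SV2.

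A reader might infer that all subjects were measured under two different diet rules, or that the primary urinary result is shown to be biased and a drug effect hidden. The documents do not support that. Only subjects above five servings are affected, their number may be zero, and how sites acted is unknown. The threshold in 8.3 is worded cautiously and is limited to rapid growth. Calcium and vitamin D supplements are already excluded. Albumin-corrected serum calcium, the other primary calcium criterion, is not shown to be affected.

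Two further points stand in part. Absolute values, shift tables, flagged out-of-range listings and the diet listing let a reader look at individual cases, though none takes account of diet. The protocol text supplied also matches the superseded wording in SAP Table 1, which cites protocol versions 4.0 and 6.0. Whether 10.8.2 was later changed cannot be seen from these documents.

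**Conclusion.** The three protocol sections need reconciling. As 10.8.2 is written, the cap follows the baseline urine, and for subjects above five servings it conflicts with the same-intake rule. For those subjects, following the cap would bias the change in 24-hour urinary calcium and in calcium:creatinine ratio downwards.

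The effect on the mean is unknown. Under the stated assumptions it lies between 0 and −27 mg/day. It is small against the confidence interval unless a substantial share of subjects exceed the cap by a wide margin, or the SD is at the low end. The effect on one subject's change or shift category (9 to 90 mg/day, assumed) is the more plausible consequence. Confidence is high that the wording is inconsistent and low on how much it mattered.

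**What to change.** **Protocol.** Reconcile 10.8.2, 8.3 and 3.1 so that the cap is given at SV1, together with the diary and urine-collection instruction and before the baseline collection. State that daily servings at SV2 are entered in the CRF. Section 10.8.2 says this explicitly only for the Visit 3 and Visit 5 reviews.

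**SAP.** Add a supplementary version of Tables 3-8 and 3-14 that excludes subjects above five servings at baseline and shows, or adjusts for, the change in daily servings from baseline. Restricting to five or fewer servings at both collections would not be enough. A subject going from five servings to one would still qualify, although intake had fallen by 4 × 300 = 1200 mg/day. If SV2 servings were not captured, the report should say so.

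**Cost.** One instruction is moved and one CRF entry made explicit, and two extra tables are produced with a somewhat smaller n. No visit or sample is added. The SAP was written after review of the data, so for data already collected only the added tables can help.

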#### ***Instruction on 24-hour urine collection***

In addition to the instructions on dietary calcium intake, the (sub)investigator/site staff should instruct the subject on how to perform the 24-hour urine collection. The procedure for collecting a 24 hour urine sample should be for subject to pass their first urine of the day as normal and then to collect all urine passed in the next 24 hours which should include their first urine on the second morning.

### **10.8.3 Clinical Assessment**

#### **10.8.3.1 Investigator Assessments**

The (sub)investigator will make the clinical assessments listed below. Ideally, all assessments for a subject should be made by the same (sub)investigator.

#### **Investigator's Global Assessment (IGA) of Disease Severity – Scalp Psoriasis and Body Psoriasis**

At SV2 and Visits 1 to 5, and early withdrawal (if applicable), the (sub)investigator will make a global assessment of the disease severity of the scalp psoriasis and body psoriasis (separately) by use of the 5-point scale below. The assessment will be based on the condition of the disease at the time of evaluation and not in relation to the condition at a previous visit.

- |                  |  |
|------------------|--|
| (0) Clear        | Plaque thickening = no elevation or thickening over normal skin
Scaling = no evidence of scaling
Erythema = none (no residual red coloration but post-inflammatory hyperpigmentation may be present) |
| (1) Almost clear | Plaque thickening = none or possible thickening but difficult to ascertain whether there is a slight elevation above normal skin level   |

- Scaling = none or residual surface dryness and scaling  
Erythema = light pink coloration
- (2) Mild      Plaque thickening = slight but definite elevation  
Scaling = fine scales partially or mostly covering lesions  
Erythema = light red coloration
- (3) Moderate      Plaque thickening = moderate elevation with rounded or sloped edges  
Scaling = most lesions at least partially covered  
Erythema = definite red coloration
- (4) Severe      Plaque thickening = marked or very marked elevation typically with hard  
or sharp edges  
Scaling = non-tenacious or thick tenacious scale, covering most or all of  
the lesions  
Erythema = very bright red coloration; extreme red coloration; or deep red  
coloration

*Note: IGA of the scalp should include all scalp psoriasis lesions, defined as those areas of the scalp where there are any signs of redness, thickness or scaliness caused by psoriasis.*

*The scalp is defined by the hair line. Parts of scalp psoriasis lesions that extend outside the defined area of the scalp should not be included in the assessments.*

At SV2 and Visit 1 the disease severity of scalp psoriasis and the disease severity of body psoriasis must be graded at least as moderate in order to meet the inclusion criteria.

Subjects with disease severity classified as “Clear” or “Almost clear” disease after the treatment period will be rated as having “Controlled disease”.

### **Investigator’s Assessment of the Extent of Psoriasis Vulgaris**

In order to obtain baseline data of psoriatic severity for all the subjects enrolled in the trial, the (sub)investigator will also assess the extent of the subject’s total psoriatic involvement at SV2 and Visit 1.

The total psoriatic involvement (e.g., the arms, the legs, the trunk, the scalp and the face) will be recorded as a percentage of the total BSA, estimating that the surface of the subject’s full, flat palm (including the five fingers) correlates to approximately 1% of the BSA.

**Investigator's Assessment of the Extent of Scalp Psoriasis**

A baseline assessment of the extent of scalp psoriasis as percentage of the total scalp area will be done at SV2 and Visit 1, estimating that the surface of the subject's full, flat palm (including the five fingers) correlates to approximately 25% of the scalp area.

**Investigator's assessment of the extent and severity of clinical signs of psoriasis vulgaris (Redness, Thickness, Scaliness)**

At SV2 and Visits 1 to 5 and early withdrawal (if applicable), the (sub) investigator will make assessments of the extent and severity of clinical signs of the subject's psoriasis on specific areas of the body in terms of three clinical signs: redness, thickness and scaliness.

The **extent** of psoriatic involvement will be recorded for each of the four areas: head\*, arms\*\*, trunk\*\*\* and legs\*\*\*\* using the following scale:

- 0 = no involvement
- 1 = < 10%
- 2 = 10 - 29%
- 3 = 30 - 49%
- 4 = 50 - 69%
- 5 = 70 - 89%
- 6 = 90 - 100%

\*) head includes the neck

\*\*) arms include hands

\*\*\*) trunk includes flexures

\*\*\*\*) legs include buttocks and feet

The **severity** of the psoriatic lesions in each of the four areas will be recorded for each of the signs of redness, thickness and scaliness. For each clinical sign, a single score, reflecting the average severity of all psoriatic lesions on the given body region, will be determined according to the scale below:

**Redness**

- 0 = none (no erythema)
- 1 = mild (faint erythema, pink to very light red)
- 2 = moderate (definite light red erythema)
- 3 = severe (dark red erythema)

4 = very severe (very dark red erythema)

#### Thickness

0 = none (no plaque elevation)  
 1 = mild (slight, barely perceptible elevation)  
 2 = moderate (definite elevation but not thick)  
 3 = severe (definite elevation, thick plaque with sharp edge)  
 4 = very severe (very thick plaque with sharp edge)

#### Scaliness

0 = none (no scaling)  
 1 = mild (sparse, fine-scale lesions, only partially covered)  
 2 = moderate (coarser scales, most of lesions covered)  
 3 = severe (entire lesion covered with coarse scales)  
 4 = very severe (very thick coarse scales, possibly fissured)

*PASI is calculated using the formula given below based on the Investigator's assessment of the extent and severity of the disease locally (head, trunk, arms, legs).*

*The following formula will be used to calculate the PASI:*

$$\begin{aligned} \text{Head} & 0.1 (R + T + S)E = W \\ \text{Arms} & 0.2 (R + T + S)E = X \\ \text{Trunk} & 0.3 (R + T + S)E = Y \\ \text{Legs} & 0.4 (R + T + S)E = Z \end{aligned}$$

*Where: R = score for redness; T = score for thickness; S = score for scaliness; E = score for extent*

*The sum of W+X + Y + Z gives the total PASI, which can range from 0 to 72.*

### 10.8.3.2 Subject Assessments

The subjects will make the following clinical assessments:

#### **Patient's Global Assessment of Disease Severity – Scalp Psoriasis and Body Psoriasis**

At SV2 and Visits 1 to 5, and early withdrawal (if applicable), the subject will make a global assessment of the disease severity of scalp psoriasis and body psoriasis (separately) by use of the 5-point scale below.

The assessment will be based on the condition of the disease at the time of evaluation and not in relation to the condition at a previous visit.

The qualified site staff person will explain the categories of the scale to the subject and the subject will tell the qualified site staff person which category to tick. This assessment must be made prior to the investigator's assessments.

